# **Protocol Summary**

This document represents the protocol summary for the study on human subjects. The study will be carried out in accordance with ICH GCP, National Standard of the Russian Federation GOST 52379-2005 "Good Clinical Practice", Helsinki Declaration of World Medical Association, relevant requirements of the regulatory authorities as well as the study procedures.

# Title of Study

Multicentre Double-blind Placebo-controlled Parallel Group Randomized Clinical Trial of Efficacy and Safety of Anaferon in the Treatment of Acute Respiratory Viral Infections *Phase:* IV *Sponsor:* OOO "NPF "Materia Medica Holding", Moscow, Russia *Protocol No.* MMH-AN-005

# **Objective of the study**

• To obtain additional data on the efficacy and safety of Anaferon in the treatment of acute respiratory viral infections (ARVI).

# Endpoints

# Primary endpoint

1. Time to resolution of ARVI symptoms (clinically diagnosed and/or PCR-confirmed).

# Secondary endpoints

- 1. ARVI severity (clinically diagnosed and/or PCR-confirmed); based on the area under the curve (AUC) data for the Total Severity (TS) score on days 1-6 of the observation).
- Percentage of patients with resolution of ARVI symptoms (clinically diagnosed and/or PCRconfirmed).
- 3. Time to resolution of ARVI symptoms (PCR-confirmed).
- 4. Percentage of patients with resolution of ARVI symptoms (PCR-confirmed).
- 5. Dosing frequency of antipyretics on days 1-3 of therapy.
- 6. The percentage of patients requiring administration of antibiotics during 4-7 days of the observation

<sup>1 Time from enrollment to symptom resolution. **Criteria of resolution of ARVI symptoms:** body/axillary temperature  $\leq$ 37.3oC for 24 hours (without subsequent increase within the observation period) + absence/presence of general ARVI symptoms with  $\leq$ 2 point of Total Severity (TS) score.

<sup>2 Total Severity (TS) index will be calculated from the rating scores obtained for each of the symptoms of ARVI (body temperature, non-specific/flu-like symptoms, and nasal/throat and chest symptoms); the subsequent data analysis will be performed by Materia Medica Holding. For TS index, absolute body temperatures (in degrees Celsius) will be converted to arbitrary units (or scores) using the following scale:  $\leq 37.3^{\circ}C=0$  points;  $37.4-38.0^{\circ}C=1$  point;  $38.1-39.0^{\circ}C=2$  points;  $\geq 39.1^{\circ}C=3$  points.

# Safety assessment

- Adverse events (AEs) during the treatment, AEs severity and relationship to the study drug, and AEs outcomes.
- Changes in vital signs during the treatment.

# Study design

Study design: multicenter, double-blind, placebo-controlled, parallel-group randomized trial.

The study will enroll patients of either gender aged 18-70 years old with clinical manifestations of ARVI within the first day after the onset of the disease. Signed information sheet for patient will be obtained from all participants prior to the screening procedures. Medical history, concomitant medication, thermometry, patient examination by a doctor, assessment of ARVI symptoms severity will be performed at screening visit.

The nasopharyngeal swabs will be performed for Real-time reverse transcription polymerase chain reaction (PCR) assay to confirm viral etiology of ARVI and to verify respiratory viruses prior to the therapy.

If a patient meets all inclusion criteria and does not have any exclusion criteria, at Visit 1 (Day 1) he/she will be randomized into one of two groups: the 1st group patients will take Anaferon according to the dosage regimen until the end of the study; the 2nd group patients will take Placebo according to Anaferon dosage regimen until the end of the study.

The patients will be provided with a patient diary (paper or electronic) where daily they will record axillary body temperature (using a Geratherm Classic thermometer) and each ARVI symptom severity twice a day (in the morning and in the evening). In addition, antipyretic administration (if applicable) as well as any possible worsening of the patient's condition (if applicable, for safety evaluation/AEs documentation) will also be recorded in a patient diary. An investigator will provide the instructions on filling out the diary and will help the patient to make first records of ARVI symptom severity and body temperature in the diary.

Patients are observed up for 7 days (screening, randomization - 1 day, study therapy - 5 days, follow-up period - 2 days). During treatment and follow-up period two visits are scheduled (at home or at the study site) on days 5 (Visit 2) and day 7 (Visit 3). At Visits 2 and 3, the investigator will carry out physical examination, record dynamics of ARVI symptoms and concomitant therapy and check patient diaries.

<sup>3 Real-time reverse transcription polymerase chain reaction (PCR) assay is carried out using the AmpliSens kit to detect the most common ARVI and influenza agents, including (1) Influenza A virus; (2) Influenza B virus; (3) Influenza A (H1N1)pdm, similar to A/California/4/2009; (4) Human metapneumovirus; (5) Human respiratory syncytial virus; (6) Human rhinovirus; (7) Human adenovirus; (8) Human bocavirus; (9) Human parainfluenza virus 1; (10) Human parainfluenza virus 2; (11) Human parainfluenza virus 3; (12) Human parainfluenza virus 4; (13) Human coronavirus OC43; (14) Human coronavirus 229E; (15) Human coronavirus HKU1; (16) Human coronavirus NL63.

Treatment compliance will be evaluated at Visit 3.

During the study, symptomatic therapy and therapy for underlying chronic conditions are allowed with the exception of the drugs indicated in the section "Prohibited Concomitant Treatment".

# Inclusion and exclusion criteria

#### Inclusion criteria

- 1. Patients of either gender aged 18-70 years.
- 2. Diagnosis of ARVI based on medical examination: axillary temperature  $\geq$  37.8°C at examination + non-specific/flu-like symptom score  $\geq$ 4, nasal/throat/chest symptom score  $\geq$ 2.
- 3. The first 24 hours after ARVI4 onset.
- 4. Seasonal rise in ARVI incidence.
- 5. Patients giving their consent to use reliable contraception during the study.
- 6. Signed patient information sheet (informed consent form).

#### Exclusion criteria

- 1. Suspected pneumonia, bacterial infection (including otitis media, sinusitis, urinary tract infection, meningitis, sepsis, etc.) requiring administration of antibacterial drugs from the first day of disease.
- Suspected initial manifestations of diseases with symptoms similar to ARVI at onset (other infectious diseases, flu-like syndrome at the onset of systemic diseases of connective tissue, oncohaematological and other diseases).
- 3. Clinical symptoms of severe influenza/ARVI requiring hospitalization.
- 4. Subjects requiring concurrent antiviral products forbidden by the study.
- 5. Medical history of primary and secondary immunodeficiency.
- 6. Oncologic conditions /suspected oncologic conditions.
- 7. Aggravation or decompensation of chronic diseases affecting a patient's ability to participate in the clinical trial.
- 8. Impaired glucose tolerance, diabetes mellitus.
- 9. Malabsorption syndrome, including congenital or acquired lactase or other disaccharidase deficiency, galactosemia.
- 10. Allergy/ hypersensitivity to any component of the study drug.

<sup>4 The time of ARVI onset is the time of manifestation of fever or febrile illness (axillary temperature  $\geq$ 37.4°C, oral or tympanic temperature  $\geq$ 37.6°C, or rectal temperature  $\geq$ 38.0°C).

<sup>5 Severe influenza/ARVI criteria (WHO 2011; CDC 2017): shock syndrome III, crucial deterioration in the general condition, decreased activity or lightheadedness up to loss of strength, severe tachycardia/bradycardia, tachypnoea, hypo-/hyperventilation, circulation disorder, peripheral cyanosis, prolonged capillary nail refill time, vomiting, dehydration symptoms, decreased urine formation/anuria, convulsions, meningism), hemorrhage (epistaxis, petechiae on the skin or in mucous membranes), haemodynamic instability, severe obstructive airway disorders (constrictive laryngotracheitis, bronchial obstruction syndrome), acute respiratory failure, primary and secondary pneumonia. Risk factors for severe influenza/ARVI and complications: chronic diseases, including cardiovascular diseases, respiratory diseases, diabetes mellitus, immunosuppression, and cancer.

- 11. Pregnancy, breast-feeding; childbirth less than 3 months prior to the inclusion in the trial, unwillingness to use contraceptive methods during the trial.
- 12. Consumption of narcotics, alcohol > 2 alcohol units per day, mental diseases.
- 13. Course administration of the drug products specified in the section "Prohibited Concomitant Therapy" within two weeks prior to inclusion in the study.
- 14. Patients who will not fulfill the requirements during the study or follow the order of administration of the studied drug products, from the Investigator's point of view.
- 15. Participation in other clinical trials for 3 months prior to enrollment in this study.
- 16. Patients who are related to any of the on-site research personnel directly involved in the study or are an immediate relative of the investigator. 'Immediate relative' means husband, wife, parent, son, daughter, brother, or sister (regardless of whether they are natural or adopted).
- 17. Patients who work for OOO "NPF "Materia Medica Holding" (i.e. the company's employees, temporary contract workers, designated officials responsible for carrying out the research or any immediate relatives of the aforementioned).

# Criteria for Withdrawal or Termination

- 1. Patient failed screening procedure.
- 2. Inability or refusal of patient to comply the Protocol requirements.
- 3. Deviation from the schedule of visits 2 and 3 for more than 1 day.
- 4. Necessity in medicines prohibited within the study.
- 5. An adverse event requiring study drug cancellation.
- 6. Desire of patient to complete the study ahead of schedule due to inefficacy of therapy or any other reason.
- 7. Pregnancy.
- 8. Cases not specified by the protocol where the investigator decides that further participation may harm the patient.
- 9. Incorrect inclusion of ineligible patient.

# Number of subjects

It is planned to include total of 204 patients (102 patients in Anaferon and Placebo groups).

# Interim analysis

The protocol does not schedule unblinded interim analyses. At the sponsor's request blinded interim analysis may be carried out to specify population parameters and potential further specification of sample size (increase only).

# Treatment

# Group 1

#### Name of the medicinal product: Anaferon

Active ingredient: affinity purified antibodies to human interferon gamma - 0.003 g\*

\* applied onto lactose monohydrate as a water-alcohol mixture containing no more than 10-15ng/g active form of the active ingredient.

**Excipients:** Lactose monohydrate -0.267 g, microcrystalline cellulose -0.03 g, magnesium stearate -0.003 g.

**Method of administration:** Tablet for oral use. Single dose – 1 tablet, to be held in the mouth until complete dissolution outside of meal (between meals or 15-30 minutes before meals). Dosing scheme. One dose every 30 minutes for the first 2 hours, followed by three more doses spaced regularly during the rest of the day. From day 2 to 5: 1 tablet taken 3 times daily. **Dosage form:** Tablets.

**Description:** White to off-white, round, flat, scored on one side and beveled tablets. **Storage conditions:** Store below 25°C. Keep out of the reach of children.

# Group 2

Name of the medicinal product: Placebo

Active ingredient: NA

**Excipients:** Lactose monohydrate -0.267 g, microcrystalline cellulose -0.03 g, magnesium stearate -0.003 g.

Method of administration: Placebo using Anaferon scheme.

Dosage form: Tablets.

Description: White to off-white, round, flat, scored on one side and beveled tablets.

Storage conditions: Store below 25°C. Keep out of the reach of children.

#### Treatment duration

Anaferon/Placebo treatment duration is 5 days.

#### **Observation period**

In total, the patient is observed up for 7 days (screening and randomization up to 1 day, therapy for 5 days, follow-up from 5 to 7 day).

#### Symptomatic (Standard) treatment

Throughout the study, patients can receive symptomatic flu/ARVI therapy based on the approved standards of care.

Indications for prescription of antipyretics:

Increased body temperature  $> 39^{\circ}$ C in subjects without complications and co-morbidities and  $> 38^{\circ}$ C in subjects with co-morbidities (congestive heart failure, hepatic, renal diseases; history of convulsive syndrome).

If antipyretic was taken by the patient on his own (without doctor recommendation) with no indications the patient is not excluded from the study. The patient should record the values of thermometry before taking the drug, its name and dose.

# Drug product allowed for use as antipyretic (the ATC group is indicated in brackets):

- Ibuprofen (M01AE01).

The antipyretic ibuprofen (Nurofen®, 200 mg tablets, Reckitt Benckiser Healthcare International Ltd.) will be provided by the Sponsor for all the participants of the study.

The investigator will be responsible for explaination dosing rules for concomitant therapy to the patient and issue the product based on the indications.

# Prohibited concomitant therapy

Two weeks before inclusion in the study\*, as well as during the study (from signing of the information sheet for patient /informed consent form) it is prohibited to administer the following drug products (their ATC group is indicated in brackets):

[figure not shown]
- 1. Antivirals (J05), except for Anaferon prescribed within this study.
- 2. Antimicrobials and antiseptics for local treatment of oral diseases (A01AB).
- 3. Medications for the treatment of throat diseases (R02A).
- 4. Immunostimulants (L03), including:
  - interferon inducers (acridonoacetic acid, meglumine acridone acetate/cycloferon®, umifenovir/arbidol®, kagocel®, tiloron/amixin®, polyadenyl acid + polyuridylic acid/poludan®, sodium oxodihydroacridinyl acetate/neovir®, lavomax®, tilaxin®, etc.)
  - interferons;
  - bacterial immunomodulators (including ribomunyl®, sodium ribonucleate/ridostin, etc., sodium deoxyribonucleate/derinat®, etc., IRS-19, imudon®, broncho-munal®, etc.).
  - pidotimod/immunorix;
  - interleukins;
  - synthetic immunostimulants (levamisole, alpha-glutamyl-tryptophan/thymogen, etc.);
  - drug products with thymus hormones.
- 5. Non-steroidal anti-inflammatory drugs (M01, except for ibuprofen).

#### CONFIDENTIAL

- 6. Analgesics and antipyretics (N02A).
- 7. Combination preparations for relief of URI symptoms.
- 8. Homeopathic preparations.
- 9. Biologically active food supplements (BAFS).
- 10. Systemic (oral or parenteral) corticosteroids.
- 11. Immunosuppressants (L04).
- 12. Antineoplastic agents (L01) and combined (with hormones) antineoplastic endocrine therapy (L02).
- 13. Immune sera and immunoglobulins (J06).
- 14. Vaccines (J07).
- 15. Drugs that previously caused hypersensitivity/ allergic reactions in patient.

\*Patients were allowed to take a single dose of prohibited medications (except for 10-14) prior to inclusion, if the interval between the medication intake and randomization was more than 12 hours.

# Study design scheme

# Schedule of study procedures

Procedure/visit	Visit 1 (Day 1)	Visit 2 (Day 5)	Visit 3 (Day 7±1)
Informed consent	+		
Registration of a study subject in the IVRS and assignment of patient ID	+		
Collection of complaints	+	+	+
Medical history	+		
Physical examination	+	+	+
ARVI symptoms registration	+	+	+
Patient Diary	+	+	+
Pregnancy test	+		
Concomitant therapy	+	+	+

CONFIDENTIAL

			20-1 v 1ay-2010
Eligibility assessment	+		
Nasopharyngeal swabs for PCR	+		
Randomization and prescription of study drug	+		
Study drug supply	+		
Concomitant medication supply	+		
Study drug accountability and return			+
Treatment compliance			+
Evaluation of treatment safety	+	+	+
Visit completion	+	+	+
Study completion			+

# **Statistical Analyses**

#### Samples

*Total set:* all patients who have signed ICF. This sample will consider all the recorded AEs, including those occurred prior to the study therapy.

*Safety population:* all patients who received at least one dose of the study drug. This sample will be used for *analysis of the study treatment safety and tolerability*, as all adverse events identified after the study drug administration will be recorded. The AEs registered in patients of the *Total set* sample from the moment of signing the Informed Consent Form, but before the test drug administration will not be taken into account when analyzing the study therapy safety.

*Full Analysis Set.* This sample includes all enrolled patients, except for those who met at least one of the following events:

- 1) non-compliance with inclusion / exclusion criteria;
- 2) the patient did not take a single dose of the study drug;
- 3) lack of any data about the patient after administration of the study drug.

This sample, the most consistent with the "Intention-to-treat" principle, will be used for the *Intention-to-treat analysis (ITT analysis)* of the study therapy efficacy.

*Per protocol set.* This sample includes all patients who have received the complex therapy under the Protocol, completed all the scheduled visits and had no significant deviations from the Protocol. This sample will be used for the *Per Protocol analysis (PP- analysis)* of the study therapy efficacy.

#### Evaluation of sample size

The sample size was assessed on the basis of the following rules and assumptions:

- 1. Statistical provisions.
  - 1.1 the power of the statistical tests " $P = (1 \beta)$ " is assumed to be 80% (the probability of correct rejection of the null hypothesis is 0.8);

- 1.2 the probability of a type I error " $\alpha$ " is allowed to be less than 5% (the probability of the erroneous acceptance of an alternative hypothesis is less than 0.05);
- 1.3 the statistical criteria used are 2-sided;
- 1.4 the calculation of the sample size is based on the assumptions about the expected effects, declared in the primary efficacy endpoint;
- 1.5 the ratio between the sample sizes of the Product and Placebo groups is 1:1 (1 Product patient - 1 Placebo patient);
- 1.6 the significance level for type I error is distributed between primary and secondary endpoints: 0.04 for the primary and 0.01 for the secondary (0.04, 0.01)
- 1.7 statistical hypotheses: null and alternative hypotheses about the superiority of the study drug over placebo using the applied dosing regimen:

primary test:

$$H_0: M_1 - M_2 = 0$$

$$H_a: M_1-M_2 \neq 0$$

where M1 – the median time to resolution of all symptoms in the Product group;

M2 – the median time to resolution of all symptoms in the Placebo group. The sample size is calculated for the Wilcoxon non-parametric test in compliance with the O'Brien-Castelloe approximation.

Programme code:

proc power;

twosamplewilcoxon

vardist("Trt") = normal(5.18,1.36)

vardist("Pl") = normal(5.84,1.28)

variables = "Trt" | "Pl"

nbins=5000

alpha=0.04

npergroup = .

power = 0.8;

run;

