# Additional test:

Null and alternative hypotheses:

$$H_0: AUC_1 - AUC_2 = 0$$
$$H_0: AUC_1 - AUC_2 \neq 0$$

where  $AUC_1$  – the area under curve in the Product group,

CONFIDENTIAL

<sup>6 Performed using the SAS software. Assessment of the parameters for distributions – refer to p.2

AUC2 – the area under curve in the Placebo group;

the sample size for statistical tests was calculated using the following formula:

$$\mathbf{n}_1 = \mathbf{k}\mathbf{n}_2$$
$$\mathbf{n}_2 = \frac{\left(z_{\alpha/2} + z_\beta\right)^2 * (1 + 1/k) * \sigma^2}{\varepsilon^2}$$

where  $n_1$ ,  $n_2$  – the sample size of the study drug and the placebo groups respectively;

 $\varepsilon = AUC_1 - AUC_2$  – the expected difference in the severity AUC between the Product and Placebo groups;

**k** – the ratio of choice between Product and Placebo (1 to 1);

 $\sigma$  – the standard deviation of the AUC;

 $z_{\alpha/2}$  – a tabulated two-tailed z-test for  $\alpha$ ;

 $z_{\beta}$  – a tabulated one-tailed z-test for  $\beta$ .

1.8 final sample size will be determined using the formula:

 $N_T = N_{PP} / (1 - C_w),$ 

where  $N_T$  – the final sample size;

 $N_{PP}$  – the value calculated in section 1.8, i.e. the expected number of the subjects completing the study per protocol;

 $C_w$  – withdrawal coefficient.

2. Assumptions about the expected effects of the clinical study.

Time to resolution of symptoms in the Product group is 5.18 days, time to resolution of symptoms in the Product group is 5.84 days.

A priori estimates for tested parameter variables in the groups

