# Study drug group:

 $T_{\rm tr} = (\langle max(N(2.6, 1.77), N(5, 1.47)) \rangle)$ 

Where < ... > stands for averaging operation, N(x,s) – normally distributed random variable with the mean x and standard deviation s. Indices: t – fever, intox – intoxication symptoms, cat - catarrhal symptoms. corresponds to the Gumbel type I distribution

for calculation of the sample size, this empirical distribution is approximated by the normal distribution with characteristics m=5.17,  $\sigma=1.36$ .

Therefore, the sample size has been found to be (71) patients in each of the groups (Product and Placebo) to estimate superiority of the study drug over placebo.

Given potential withdrawal of at least 30% subjects ( $C_w=0.3$ ) during the study for various reasons, at least 204 subjects will be required to sign informed consent, 102 per group (see. 1.8).

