#### Parametric criteria

The application of parametric criteria will be accompanied by a check for normality of the compared samples (Kolmogorov-Smirnov test).

The following parameters and approaches are to be used:

- To evaluate the differences of continuous variables obtained in one group at two different visits – Student's test for matched samples.
- 2. To evaluate the temporal dynamics of the compared indicators analysis of variance (ANOVA) or covariance (ANCOVA) in the modification with repeated measures.
- 3. In case of multiple comparisons between the groups will apply a variety of corrections for multiplicity (Dunnett), (Tukey), (Scheffe), Holm adaptive test, etc.

<sup>8 On the distribution of the maximum of N independent normal random variables: IID and INID cases. SDSSU Multidisciplinary Research Journal Vol. 1 No. 2, 2013

- 4. In case of abnormal data distribution, approaches with the Generalized Linear Models and / or Mixed Linear Models will be used.
- 5. Selection of the type of distribution, clarification of the factor and covariance structures of the model is carried out with fit statistics such as AIC (Akaike information criterion).

To perform the above-mentioned statistical tests and techniques, it is assumed that the following SAS procedures are used:

- UNIVARIATE check for normality of the compared distributions;
- CORR, MEANS calculation of descriptive statistics;
- TTEST Student t-test with all the modifications;
- GLM analysis of Generalized Linear Models for studying temporal dynamics (ANOVA, ANCOVA);
- GENMOD analysis of Generalized Linear Models.
  MIXED analysis of Generalized Linear Models.

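### The 0.04/0.01 alpha split does not say how six secondary endpoints share the 0.01, and it never releases the 0.04 after a significant primary; an alpha-passing rule gives AUC more power within the same 5%

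*Combined protocol and SAP*

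**What the plan says.** Evaluation of sample size, item 1.2, sets the ceiling: the type I error "is allowed to be less than 5" per cent. Item 1.3 makes all tests two-sided. Item 1.6 then divides the error: "the significance level for type I error is distributed between primary and secondary endpoints: 0.04 for the primary and 0.01 for the secondary". The SAS code for the primary endpoint uses 0.04 accordingly.

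The Secondary endpoints section lists six, from AUC of the Total Severity score (no. 1) to "The percentage of patients requiring administration of antibiotics during 4-7 days of the observation" (no. 6). It gives no order of testing and no division of the 0.01.

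Only AUC has a stated hypothesis, under Additional test. Its sample-size formula uses "a tabulated two-tailed z-test for" alpha without saying which alpha. It also uses "the expected difference in the severity AUC between the Product and Placebo groups" and the AUC standard deviation as symbols without values.

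The only other text on multiplicity is Parametric criteria, item 3: "In case of multiple comparisons between the groups will apply a variety of corrections for multiplicity (Dunnett), (Tukey), (Scheffe), Holm adaptive test, etc".

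**The concern.** There are two separate problems.

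**The threshold for a secondary claim is undefined.** Item 1.6 can mean 0.01 for all six together, 0.01 for AUC alone, or 0.01 for each. An equal share of a 0.01 total is 0.01/6 = 0.0017. A secondary p-value between about 0.002 and 0.01 could therefore be claimed or not, depending on a reading chosen after the data are seen. The third reading need not respect the 5% ceiling.

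**Power is given up with no gain in error control.** Under all three readings, the 0.04 spent on the primary is lost to the secondaries even when the primary is significant. Rules that carry it forward keep the same 5%, so AUC, the first-listed secondary, is tested more strictly than necessary.

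Parametric criteria, item 3, does not resolve either problem. Dunnett, Tukey and Scheffe deal with comparisons among several groups, and this trial has two. Holm could work across endpoints, but nothing selects it, ties it to the six endpoints or states its alpha.

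**Working it through.** **Inputs from the plan.** Two-sided alpha is 0.04 for the primary and 0.01 for the secondaries, with six secondaries. Primary mean (SD) is 5.18 (1.36) on drug and 5.84 (1.28) on placebo. There are 71 per arm before, and 102 per arm after, allowance for 30% withdrawal.

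**Assumptions, because the plan gives none.** The standardised AUC effect is d = 0.3, 0.4, 0.5 or 0.6. The correlation between the primary and AUC test statistics is 0.3 to 0.7.

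**1. The plan's own figure.** The O'Brien–Castelloe Wilcoxon calculation with the coded inputs at alpha 0.04 gives 71 per arm (power 0.8016). Then 71/0.7 = 101.4, which rounds up to 102 per arm, or 204 in total. The stated size reproduces.

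**2. Family-wise error under each reading.**
- 0.01 in total, or for AUC alone: at most 0.04 + 0.01 = 0.05. With equal shares of 0.01/6 and independence: 1 − 0.96 × (1 − 0.01/6)^6 = 0.0496.
- 0.01 for each: the bound is 0.04 + 6 × 0.01 = 0.10. With independence: 1 − 0.96 × 0.99^6 = 0.0962. With equicorrelated normal statistics, by numerical integration: 0.090, 0.079, 0.064 and 0.046 at correlation 0.3, 0.5, 0.7 and 0.9.

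**3. AUC power under the fixed split.** Power = Φ(d√(n/2) − z), with z = 2.576 at 0.01 and 3.144 at 0.01/6. For d = 0.5 and n = 71, d√(n/2) = 2.979. Power is Φ(0.403) = 0.657 at 0.01 and Φ(−0.165) = 0.435 at 0.01/6.

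**4. AUC power with alpha passing** (primary at 0.04; AUC at 0.05 if the primary is significant, otherwise at 0.01). Add to the 0.01 power the probability that the AUC statistic lies between 1.960 and 2.576 and the primary is significant. The planned primary effect is 0.66/√((1.36² + 1.28²)/2) = 0.4998 SD. Its noncentrality is 0.4998 × √(n/2) × √(3/π), which is 2.910 at n = 71 (power 0.804) and 3.488 at n = 102 (power 0.924).

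| n per arm | d | 0.01/6 | 0.01 | Alpha passing |
|---|---|---|---|---|
| 71 | 0.3 | 9% | 22% | 40–42% |
| 71 | 0.4 | 22% | 42% | 62–63% |
| 71 | 0.5 | 43% | 66% | 79–80% |
| 71 | 0.6 | 67% | 84% | 89–91% |
| 102 | 0.3 | 16% | 33% | 56–57% |
| 102 | 0.4 | 39% | 61% | 80% |
| 102 | 0.5 | 67% | 84% | 92–93% |
| 102 | 0.6 | 87% | 96% | 97–98% |

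The rows at 102 are an upper limit, because "at least 204 subjects will be required to sign informed consent, 102 per group" counts subjects before withdrawals.

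**5. Error control of the alpha-passing rule.** If the primary null is true, a false rejection needs either a false primary (at most 0.04) or a false secondary at level 0.01, so at most 0.05 in all. If the primary null is false, the secondaries are tested in sequence at no more than 0.05. Simulation of the primary and AUC under the global null gives 0.041–0.050 for correlations 0 to 0.9.

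**6. Holm alternative.** Holm over all six secondaries is applied at a total of 0.05 after a significant primary and 0.01 otherwise. With d = 0.5, n = 71 and no effect on the other five, AUC power is 0.60–0.61, against 0.43 for Holm within a fixed 0.01.

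**The case against.** The fixed split is a valid, conservative choice. The primary is untouched, and not recycling alpha is a lost opportunity on a secondary endpoint rather than an error. That is right, and no error-rate fault is alleged under the first two readings.

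The 10% figure rests on the reading that fits the text least. Item 1.6 speaks of distributing the error, its two figures sum to 0.05, and item 1.2 caps the total. Several secondaries also overlap heavily, so independence is a worst case. This stands as to likelihood, but the text does not exclude that reading, and error exceeds 5% on it up to a common correlation of at least 0.7. Parametric criteria, item 3, does show an intention to correct, but not how.

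The size of the gain depends on the primary succeeding. Both outcomes come from the same diary, so a weak AUC effect may accompany a weak primary effect. With the primary effect set equal to AUC's, alpha passing at 71 per arm gives 31–33% at d = 0.3 and about 57% at d = 0.4, instead of 40–42% and 62–63%. With a primary effect of only 0.2, AUC power at d = 0.5 moves from 66% to only 66–68%. This stands: the gain can be small. It is never negative, because AUC is never tested below 0.01.

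The Holm alternative can lower AUC power: about 60%, against 66% if item 1.6 meant 0.01 for AUC alone. This also stands, and it is a reason to prefer the ordered rule if AUC matters most.

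**Conclusion.** The concern holds. The plan fixes 0.04 and 0.01, does not say how six secondary endpoints share the 0.01, and never releases the 0.04 after a significant primary. Family-wise error is within 5% if 0.01 is the secondary total or AUC's alone. It is bounded only by 10% if each secondary is tested at 0.01.

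Across assumed AUC effects of 0.3 to 0.6 at 71 per arm, with the primary effect as planned and correlation 0.3 to 0.7, alpha passing adds roughly 5 to 21 percentage points over 0.01 for AUC. The direction of the gain does not depend on those assumptions; its size does. Whether AUC falls short of 80% power under the present split cannot be established, because the plan gives no AUC difference or SD. The primary test, its alpha and the sample size are unaffected. This is a change that should be made, but it does not threaten the primary conclusion.

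**What to change.** Amend item 1.6 to one stated procedure:

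1. Test the primary endpoint at 0.04, two-sided.
2. If it is significant, test AUC at 0.05; otherwise test AUC at 0.01.
3. Test the other five secondaries in a fixed, listed order at the level AUC was tested at, only after AUC succeeds and stopping at the first failure, or declare them descriptive.

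If gating on AUC is not wanted, apply Holm to all six at a total of 0.05 after a significant primary and 0.01 otherwise. In either case, state the alpha used in the AUC formula, and state in Parametric criteria, item 3, that Dunnett, Tukey and Scheffe are not used for multiplicity across endpoints.

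The cost is a wording amendment before unblinding, with primary alpha and sample size unchanged. The ordered rule requires a committed order, and if AUC fails, the other five, including both PCR-confirmed endpoints, become descriptive. The Holm version avoids that gate but gives AUC less power than the ordered rule.
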